5.9.2 Medications to be Avoided or Taken with Caution

The following medications should be avoided or taken with caution during the course of the study:

- Due to the high protein binding of ABSK021, close monitoring is required if warfarin is required.
- Low molecular weight heparin should be used under monitoring.
- For the use of H2-receptor antagonists, such as ranitidine, famotidine, or cimetidine, ABSK021 should be administered 2 hours before or 10-12 hours after H2-receptor antagonist administration.
- Gastric antacids such as aluminum hydroxide/magnesium hydroxide/dimethylsilicone oil or calcium carbonate should be avoided whenever possible but, if necessary, these medications should be administered 2 hours before or after ABSK021 administration.
- CYP2C9 and CYP2C19 substrates should be used with caution during treatment with ABSK021 (reference: <https://www.fda.gov/drugs/drug-interactions-labeling/drug-development-and-drug-interactions-table-substrates-inhibitors-and-inducers>).

5.9.3 Prohibited Medications and Substances

The following medications are prohibited during the course of the study:

- Strong inhibitors or inducers of cytochrome CYP3A4 are prohibited from 14 days prior to the initial dose of ABSK021 until the end of treatment with ABSK021 (reference: <https://www.fda.gov/drugs/drug-interactions-labeling/drug-development-and-drug-interactions-table-substrates-inhibitors-and-inducers>).

- Proton pump inhibitors, such as omeprazole, esomeprazole, lansoprazole, pantoprazole, rabeprazole, or dexlansoprazole, are prohibited from 7 days prior to the initial dose of ABSK021 until the end of treatment with ABSK021.
- Antitumor therapies other than ABSK021 (including traditional Chinese medicine preparations).
- Study drugs other than ABSK021 or any kind of investigational therapy.
- Patients are prohibited from heavy alcohol consumption (more than 2 standard alcohol consumption per day, equivalent to alcohol consumption of more than 20 grams per day or more than 140 grams per week) since at least 7 days prior to the first dose of ABSK021 throughout the study treatment period.
- Cannabis drugs (e.g., medical marijuana), whether used as medication or for other purposes, are prohibited.

6 Study Procedures

6.1 Study Schedule

The specific study procedures are presented in [Table 1](#), [Table 2](#), [Table 3](#) and [Table 4](#) describes the PK sample collection time points. The following subsections detail the study procedures such as efficacy, safety, PK assessments, in this study.

The Investigator may request additional safety or efficacy assessments to determine the relationship between the onset or duration of a clinical event and the study drug.

6.2 Randomization

In Part 1 of the study, patients will be randomized in a 2:1 ratio to ABSK021 group or matching placebo group. Randomization will be stratified by China sites and non-China sites. Please refer to [5.6](#) for randomization.

6.3 Efficacy Evaluation

Efficacy evaluations in Part 1 will be performed according to the schedule shown in [Table 1](#), and efficacy evaluations in Part 2 will be performed according to the schedule shown in [Table 2](#). In Part 3, MRI examinations will be performed as shown in [Table 3](#). Once every 3 months in the first 6 months, and then once every 6 months until the end of the study. The MRI examination results will be assessed by the Investigator and BIRC (optional) separately. Additional measurements may be performed at the discretion of the Investigator based on the actual situation.

6.3.1 Tumor Response Evaluation (Part 1)

All MRI examination results will be evaluated by BIRC and Investigators according to

RECIST v1.1, respectively. In addition, all MRI examination results will be evaluated by BIRC based on TVS for tumor response. For patients who have disease progression (including radiographic disease progression or clinical progression) as assessed by the Investigator, the radiographic disease progression will be confirmed by BIRC. The specific reading procedures will be specified in the BIRC charter.

6.3.1.1 Response per RECIST v1.1 criteria

All MRI scans will be assessed according to RECIST v1.1 by BIRC and Investigator, respectively. Patient eligibility will be determined by the Investigator based on baseline MRI findings, and all subsequent MRI findings in Part 1 will be assessed separately by the Investigator and BIRC in a manner blinded to treatment assignment. Since Part 1 is a randomized controlled study, patients who achieve complete response (CR) or partial response (PR) per RECIST v1.1 do not need to be confirmed. A patient who has a tumor assessment of PR at Week 13 and subsequently has neither sufficient shrinkage to achieve CR nor sufficient increase to achieve PD (i.e., non-CR/non-PD/non-NE) at Week 25 will be considered as PR in efficacy endpoint evaluation. The evaluation details are shown in [Table 6](#) below.

Table 6 Definition of Efficacy Responses in TGCT Patients (Part 1)

Response at Week 13	Response at Week 25	Tumor response
CR or PR	CR	Response (CR)
CR or PR	PD	Non-response (PD)
PR	Non-CR/Non-PD/Non-NE	Response (PR)
SD	CR or PR	Response (CR or PR)
SD	SD	Non-response (SD)
SD	PD	Non-response (PD)
CR, PR, SD or NE	NE	Non-response (NE)
PD	Any	Non-response (PD)
NE	CR or PR	Response (CR or PR)
NE	SD or PD	Non-response (SD or PD)

CR = complete response; NE = Not evaluable (including MRI scan is not done); PD = progressive disease; PR = partial response; SD = stable disease

All MRI scans assessed by BIRC will be read in a blinded manner according to the procedures outlined in a separate BIRC charter.

6.3.1.2 Response per TVS criteria

MRI findings will also be assessed by BIRC in a blinded manner based on tumor volume score (TVS), a novel evaluation system specifically developed for TGCT. TVS is a semi-quantitative MRI scoring system that describes tumor mass and is an extension of the 4-point synovitis scale of the well-established and widely used multifeatured score RAMRIS, originally developed for rheumatoid arthritis, and WOMBS, originally developed for osteoarthritis. The extended scale, the TVS, will be based on 10% increments of the estimated volume of the maximally distended synovial cavity or tendon sheath involved. Thus, a tumor that is equal in volume to that of a maximally distended synovial cavity or tendon sheath will be scored 10, whereas a tumor that is 70% of that volume will be scored 7, a tumor that is twice the volume of the maximally distended synovial cavity or tendon sheath will be scored 20, and so on. A score of “0” means no evidence of tumor. Individual patient outcomes by TVS will be classified according to the following criteria inspired by RECIST v1.1:

- Complete response: Lesion completely gone.
- Partial response: $\geq 50\%$ decrease in volume score relative to baseline.
- Progressive disease: $\geq 30\%$ increase in volume relative to lowest score during the study whether at baseline or some other visit.
- Stable disease: Tumor volume decrease does not meet the above criteria for PR or volume increase does not meet the above criteria for PD.
- NE: TVS not evaluable due to inadequate imaging or imaging missing.

TVS-based tumor response assessments are similar to RECIST v1.1 and will be assessed according to Table 6. All MRI scans will be read in a blinded manner according to the procedures outlined in a separate BIRC charter.

6.3.2 Tumor Response Evaluation (Part 2)

In Part 2, all MRI scans will be assessed according to RECIST v1.1 by BIRC and Investigator, respectively. In addition, all MRI scans will be assessed by BIRC for tumor response per TVS.

Readings of MRI scans will be performed during or after the patient completes the study. For patients with Investigator-assessed disease progression (including radiographic disease progression or clinical progression), radiographic disease progression will be confirmed by BIRC.

Specific reading procedures will be specified in the BIRC Charter.

6.3.3 Tumor Response Evaluation (Part 3)

In Part 3, MRI examinations will be performed once every 3 months for the first 6 months, and once every 6 months thereafter until the end of the study. All MRI examination results will be

evaluated by the Investigators according to RECIST v1.1. In addition, all MRI examination results will be evaluated by BIRC according to RECIST v1.1 and TVS as needed (optional).

Readings of MRI scans will be performed during or after the patient completes the study. For patients who are assessed to have disease progression by the Investigator (including radiographic disease progression or clinical progression), the patient's radiographic disease progression can be confirmed by BIRC as needed (optional). Specific procedures will be stipulated in the BIRC Charter.

6.3.4 Range of motion (ROM) assessment

For patients in Part 1, the range of motion of the affected joint or tumor site will be assessed using a goniometer under blinded conditions. Measurements will be recorded in degrees. The assessments will be performed at time points specified in [Table 1](#).

For patients in Part 2, the mobility of the same affected joint will continue to be assessed in the same manner as Part 1 under open-label conditions. Measurements will still be recorded in degrees. The assessments will be performed at time points specified in [Table 2](#).

For patients in Part 3, the mobility of the same affected joint will continue to be assessed in the same manner as Part 1 and Part 2 under open-label conditions. Measurements will still be recorded in degrees. The assessments will be performed at time points specified in [Table 3](#).

Measurements of ROM will be standardized by a ROM standard reference value to obtain relative ROM values. Relative ROM value = $100 \times (\text{absolute ROM value}) / (\text{ROM standard reference value})$ ²⁶.

6.3.5 Patient-Reported Outcome (PRO) Assessment

6.3.5.1 Worst Stiffness Numeric Rating Scale (Worst-Stiffness-NRS)

Stiffness will be assessed using the Worst-Stiffness-NRS. Patients will be asked to recall the degree of stiffness at the tumor site over the past 24 hours. On all study visit days requiring a Numerical Rating Scale, including the screening, the patients are recommended to complete the evaluation of the Numerical Rating Scale prior to any invasive clinical procedure. Please refer to [Table 1](#), [Table 2](#) and [Table 3](#) for specific assessment time points, and [Appendix 12.5](#) for a sample instrument.

The mean score of evaluations completed prior randomization (at least 4 of 7 consecutive days during the 2 weeks prior to randomization) and on C1D1 will be used as baseline. If there are multiple consecutive 7-day assessments, baseline will be calculated from the most recent 7-day assessments as well as C1D1. In addition, mean score (at least 4 of 7 consecutive days) of Worst-Pain-NRS ≥ 4 or mean score (at least 4 of 7 consecutive days) of Worst-Stiffness-NRS ≥ 4 within 2 weeks prior to randomization (not include C1D1) is required for eligibility confirmation.

6.3.5.2 Worst Pain Numeric Rating Scale (BPI-Worst-Pain-NRS)

For the BPI-Worst-Pain-NRS assessment, patients will be asked to recall their worst pain at the tumor site over the past 24 hours. On all study visit days requiring a Numerical Rating Scale, including the screening, the patients are recommended to complete the evaluation of the Numerical Rating Scale prior to any invasive clinical procedure. Please refer to [Table 1](#), [Table 2](#) and [Table 3](#) for specific assessment time points, and Appendix 12.4 for a sample instrument.

The mean score of evaluations completed prior randomization (at least 4 of 7 consecutive days during the 2 weeks prior to randomization) and on C1D1 will be used as baseline. If there are multiple consecutive 7-day assessments, baseline will be calculated from the most recent 7-day assessments as well as C1D1. In addition, mean score (at least 4 of 7 consecutive days) of Worst-Pain-NRS ≥ 4 or mean score (at least 4 of 7 consecutive days) of Worst-Stiffness-NRS ≥ 4 within 2 weeks prior to randomization (not include C1D1) is required for eligibility confirmation.

6.3.5.3 PROMIS Physical Functioning Scale score

The PROMIS Physical Functioning Scale includes two different sets of topics for the upper (see Appendix 12.6 for example) and lower extremities (see Appendix 12.6 for example). Items assessing lower extremity function will be used for patients with lower extremity tumors, and the items for assessing upper extremity function will be used for patients with upper extremity tumors. The mean score of evaluations during the screening period (within 14 days prior to randomization) and on C1D1 will be used as baseline. On all study visit days requiring an evaluation scale, including the screening, the patients are recommended to complete the evaluation of the evaluation scale prior to any invasive clinical procedure(s). Please refer to [Table 1](#), [Table 2](#) and [Table 3](#) for specific assessment time points.

6.3.5.4 EQ-5D-5L Health Scale Score

The EQ-5D-5L (EuroQol Working Group, www.euroqol.org) is a preference-based general health status or health-related quality of life instrument consisting of two parts. The first part comprises five domains (mobility, self-care, usual activities, pain/discomfort, and anxiety/depression) each of which can have five levels ranging from no problems through profound difficulties. The second part of the EQ-5D-5L is a Visual Analogue Scale on which the patient rates their current health, with 0 representing the “worst health you can imagine” and 100 representing the “best health you can imagine.”

The EQ-5D-5L health scale will be performed at the time points indicated in [Table 1](#), [Table 2](#) and [Table 3](#). The mean score of evaluations during the screening period (within 14 days prior to randomization) and on C1D1 will be used as baseline. On all study visit days requiring an evaluation scale, including the screening, the patients are recommended to complete the evaluation scale prior to any invasive clinical procedure(s).

6.3.6 Progressive Disease Follow-up

Patients who discontinue treatment prematurely for reasons other than disease progression will be followed for disease progression until disease progression, death, loss to follow-up, or the patient receives alternative anti-tumor therapy (including surgery), whichever occurs first. Disease progression follow-up will be conducted every 12 weeks (± 7 days). In principle, the maximum follow-up time will not exceed 12 months.

For patients who withdraw from the study after prematurely treatment discontinuation and plan to undergo surgery, it is recommended to perform the surgery at least 3 weeks after the last dose (for patients in Part 1, the Investigator and the sponsor will jointly decide whether emergency unblinding is needed). Details of the surgery will be collected, including but not limited to, the reason for surgery, date, surgery name, copies of the surgical report and pathological reports (if any), ROM and PRO assessments (if any). Surgically resected tumor samples will be collected to assess the effect of this study drug on tumor cells, and disease recurrence will also be followed up by telephone (every 3 months) for a maximum follow-up period up to 12 months after the surgery (not applicable for placebo-treated patients).

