25. Tumor imaging (MRI) will be performed at screening, on C4D1 (± 7 days), and C7D1 (± 7 days). MRI results within 28 days prior to dosing will be used as baseline, and the first tumor response evaluation will be performed on Day 4 Cycle Day 1 (C4D1 ± 7 days). At EOT visit, a corresponding tumor imaging assessment should be performed. A central review of resectability will be conducted at screening by at least one independent expert who is not part of the trial conduct.
26. The range of motion (ROM) of the affected joint or tumor site will be assessed using a goniometer according to local standard measurement methods. Measurements will be recorded in degrees. Assessments will be performed during the screening period, on C4D1 (± 7 days), and C7D1 (± 7 days). At EOT visit, a corresponding range of motion measurement of the joint should be performed.

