5.7.2 Unblinding

5.7.2.1 Emergency Unblinding

In case of emergency where, in the opinion of the Investigator, immediate unblinding of treatment is necessary in order to evaluate further course of action, the Investigator should access the IWRS to initiate patient unblinding. Whenever possible, the Investigator should communicate emergency unblinding with the sponsor as early as possible. Under the premise of the patient's safety, the unblinding should be limited to the minimum number of personnel.

The Investigator should enter in the IWRS system:

- Confirm to continue with unblinding
- Patient ID

The IWRS will provide:

- Patient's randomized treatment group
- IWRS transaction confirmation

The Investigator may also contact the sponsor's medical monitor for information related to ABSK021 adverse effects in making the decision to unblind. It is important to note that, once unblinded, a patient cannot receive further study treatment and must discontinue from the study.

The Investigator should promptly document and report to the Sponsor any unblinding for emergency reasons (e.g., accidental unblinding, unblinding due to SAE, etc.).

In the event of an emergency unblinding, the date and reason for unblinding must be fully documented in the source document and eCRF. The Investigator should make every effort to ensure that study site personnel do not mention patient treatment group assignment to sponsor staff or relevant personnel involved in the conduct of the study.

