7.1 Sample Size Determination

The sample size of this study is calculated based on the primary objective of the study, which is to compare the objective response rate within 25 weeks after treatment with ABSK021 or placebo in TGCT patients.

The target ORR of 40% for ABSK021-301 was anticipated from this study (i.e., 85% of the lower limit of 95% CI for interim ORR in ABSK021-101) based on the following considerations: a) Limited sample size in ABSK021-101 interim analysis; b) The inclusion of TGCT patients in the Phase 3 study will be more stringent than ABSK021-101 study which could lead to the enrolment of patients with a more severe condition. This may have a detrimental influence on treatment effectiveness; c) A single region preliminary ORR results from ABSK021-101 may not completely reflect the true response from the multi-region trial in a placebo control study.

Patients will be randomized in a 2:1 ratio to ABSK021 treatment group or placebo group. Assuming a 25-week ORR of 6% (P_0) (the upper 95% CI of the placebo group in the ENLIVEN study²³) in the placebo group and 40% (P_1) for ABSK021, by using Fisher's exact test with a two-sided significance level α of 0.05, a sample size of 75 evaluable patients provides a 90% power to detect the difference in the ORR between the two groups ($H_0: P_1 = P_0$ vs. $H_a: P_1 \neq P_0$). The power is calculated using the binomial distribution enumeration method (PASS 2021, v21.0.3). Considering a dropout rate of about 15%, approximately 90 TGCT patients need to be enrolled, including 60 patients in the ABSK021 treatment group and 30 patients in the placebo group.

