7.4.4.1 Primary Estimand

7.4.4.1.1 Definition of Primary Estimand

- **Population:** Patients with TGCT who meet the eligibility criteria.
- **Treatment:** Randomized treatment (ABSK021 or placebo).
- **Variable:** Objective Response (OR) within 25 Weeks based on RECIST v1.1 as assessed by BIRC in Part 1. OR is defined as the patients achieving the best overall response of CR or PR.
- **Intercurrent Events and Management Strategies**

Table 7 Intercurrent Events and Management Strategies for Estimated Objectives

Intercurrent Events	Management Strategy	Comments
Dose modifications (including dose interruption and dose reduction) due to toxicity	Treatment policy strategy Continue to collect and use the data even if the patient experiences intercurrent events.	Reflects clinical practices.
Early discontinuation of treatment not due to PD	Treatment policy strategy Continue to collect and use the data even if the patient experiences intercurrent events.	Patients who discontinue treatment prematurely not due to PD in Part 1 will be encouraged to remain in the study and followed up as scheduled until complete study Part 1.
Receiving an alternative anti-tumor therapy (including surgery)	While on treatment strategy Data before the intercurrent event will be used.	Focus on treatment effects before the intercurrent event, outcomes after the intercurrent event are regarded as unrelated to the treatment.

- **Population-level summary:** Treatment difference (ABSK021 – Placebo) in 25-Week ORR by BIRC (RECIST v1.1)

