4.2.4. Definition of Analysis Windows

The window for the visits following baseline will be constructed in such a way that the upper limit of the interval falls halfway between the two visits (the lower limit of the first post-baseline

Statistical Analysis Plan for Protocol ABSK-021-301

visit will be Day 2). If an even number of days exists between two consecutive visits then the upper limit will be taken as the midpoint value minus 1 day.

The following rules will be applied to assign actual patient visits to protocol-specified visits. For each protocol-specified study visit, a target study day will be identified to represent the corresponding visit along with a window around the target day. Windows will be selected in a non-overlapping fashion so that a collection date does not fall into multiple visit windows. If a patient has two or more actual visits in one visit window, the visit closest to the target day will be used for analysis. If two visits are equidistant from the target day, then the later visit will be used for analysis.

The visit window and the target study day from Part 1 for each protocol-specified visit are displayed in [Table 4.2](#) and [Table 4.3](#) (depending on the different visit schedules of different endpoints).

Table 4.2 Analysis Windows for PRO endpoints and Range of Motion

Study Period	Protocol Specified Visit	Target Day	Visit Window Range [min, max]		
			Worst Stiffness NRS, BPI Worst Pain NRS, PROMIS-PF and EQ-5D-5L	Range of Motion	NCI-PRO-CTCAE
Part 1	Baseline	1[a]	[-28, 1]	[-28, 1]	[-28, 1]
	Week 2 (C1D8)	8			[2,11]
	Week 3 (C1D15)	15			[12, 18]
	Week 4 (C1D22)	22			[19,25]
	Week 5 (C2D1)	29	[2, 43]		[26, 32]
	Week 6 (C2D8)	36			[33,39]
	Week 7 (C2D15)	43			[40, 46]
	Week 8 (C2D22)	50			[47, 53]

Statistical Analysis Plan for Protocol ABSK-021-301

Study Period	Protocol Specified Visit	Target Day	Visit Window Range [min, max]		
			Worst Stiffness NRS, BPI Worst Pain NRS, PROMIS-PF and EQ-5D-5L	Range of Motion	NCI-PRO-CTCAE
	Week 9 (C3D1)	57	[44, 71]		[54, 71]
	Week 13 (C4D1)	85	[72, 99]	[2, 127]	[72, 99]
	Week 17 (C5D1)	113	[100, 127]		[100, 127]
	Week 21 (C6D1)	141	[128, 155]		[128, 155]
	Week 25 (C7D1)	169	[156, 1st dose date of Part 2 or 184]	[128, 1st dose date of Part 2 or 184]	[156, 1st dose date of Part 2 or 184]
Part 2	Week 25 (C1D1)[b]	169	[156, 1st dose date of Part2]		
	Week 29 (C2D1)	197	[1 day after 1st dose date of Part 2, 211]		
	Week 33 (C3D1)	225	[212, 239]		

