6.3.2. Handling of Dropouts and Missing Data

If patients withdraw consent from the study before the Week 25 visit, no further data will be collected, and only tumor scans up until the date of withdrawn consent will be included in the evaluation of tumor response. Missing MRI data will not be imputed. Patients with missing MRI data at the Week 25 visit will be considered as non-responders.

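### The Part 1 visit schedule does not secure the Week 25 MRI and range-of-motion data that the treatment-policy estimands rely on

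*Protocol*

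**What the plan says.** **The commitment.** Protocol Table 7 applies treatment policy to dose modification for toxicity and to stopping treatment for reasons other than progression (PD). Patients who stop for such reasons "will be encouraged to remain in the study and followed up as scheduled until complete study Part 1". Protocol 7.4.4.1.2 includes the data collected after they stop, and SAP 6.4.2 strongly encourages them to attend every visit. For ROM, the estimand in SAP 1.1 goes further and applies treatment policy to stopping because of PD and to alternative anti-tumor therapy as well.

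**The instructions to sites.**
- Protocol 6.3.6 and Table 1 footnote 5 cover patients who stop for reasons other than PD: "Disease progression follow-up will be conducted every 12 weeks", within 7 days either side. They name no starting date and no Week 25 visit, and this follow-up ends at alternative therapy.
- Table 1 marks imaging, but not ROM, under Progression Follow-up.
- After listing the scheduled ROM visits, footnote 26 adds only: "At EOT visit, a corresponding range of motion measurement of the joint should be performed". Footnote 25 does the same for MRI. Footnotes 27 and 28 recommend pain, stiffness, PROMIS and EQ-5D-5L assessments up to Week 25 even after progression or discontinuation.
- Protocol 5.7.2.1 on emergency unblinding: "once unblinded, a patient cannot receive further study treatment and must discontinue from the study". Table 7 does not list unblinding as an intercurrent event.

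**The scoring rule.** SAP 6.3.2: "Patients with missing MRI data at the Week 25 visit will be considered as non-responders". Protocol Table 6 and SAP Table 6.1 apply this even when Week 13 was CR or PR.

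**The concern.** A treatment-policy estimand needs outcome data after treatment stops. Here the statistical sections assume that those data exist, while the schedule and footnotes that sites work from do not ask for them clearly. The sponsor wrote the necessary sentence for the patient-reported outcomes, but not for the MRI behind the primary endpoint and the first key secondary endpoint (TVS response), nor for ROM, the second key secondary endpoint.

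A site that follows footnote 5 and Section 5.7.2.1 literally can lose the Week 25 scan of a patient who responded at Week 13, and that patient is then counted as a non-responder. For ROM, the value becomes missing and the mixed model relies on a missing-at-random assumption. Neither result is what treatment policy describes, and off-treatment measurements cannot be recovered later.

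**Working it through.** **1. The plan's own figure.** Inputs from Protocol 7.1: response rates of 40% and 6%, Fisher's exact test, "two-sided significance level α of 0.05", 2:1 allocation, and "a sample size of 75 evaluable patients provides a 90% power to detect the difference in the ORR between the two groups". Seventy-five patients at 2:1 is 50:25. Power is the sum, over all pairs (x, y) with Fisher p ≤ 0.05, of Bin(x; 50, 0.40) × Bin(y; 25, 0.06).
- Doubling the smaller one-sided p: 90.3%, which reproduces the stated 90%.
- The usual two-sided p (sum of table probabilities no larger than the observed one): 92.3%.
- Enrolment: 75 / 0.85 = 88.2, rounded up to 89; the plan says about 90.

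**2. Do the 12-week scans reach Week 25?** The Week 25 window is Day 169 ± 7, that is Days 162 to 176. Take a patient who stops on day s, from 1 to 161, and count scans at s + 84k.
- Cycle run from an end-of-treatment scan on the stop day: k = 2 hits the window for s = 1 to 8 (162 − 168 = −6; 176 − 168 = 8). k = 1 hits it for s = 78 to 92 (162 − 84; 176 − 84). That is 8 + 15 = 23 of 161 stop days.
- Using the full 7 days allowed for the end-of-treatment visit and the ±7 days on each later scan: s = 1–15, 64–99 and 155–161, or 15 + 36 + 7 = 58 of 161.
- Cycle run from the scheduled Week 13 scan (Day 85): 85 + 84 = 169, exactly Week 25.

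The unstated starting point therefore decides whether the progression scans supply a Week 25 MRI.

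**3. ROM.** The last ROM after stopping is at the end-of-treatment visit, due within 7 days. SAP Table 4.2 opens the Week 25 ROM window on Day 128. A patient who stops before about Day 121 (128 − 7) has no Week 25 ROM unless the Table 7 commitment is followed.

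**4. Size for the primary endpoint.** The documents give no rate of early stopping or unblinding. Assume a share d lacks the Week 25 scan independently of response, so each response rate is multiplied by (1 − d). With 60:30 randomised:

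| Scenario | Rates | Difference (points) | Power, usual p | Power, doubled p |
|---|---|---|---|---|
| No loss | 40% vs 6% | 34.0 | 96.7% | 95.6% |
| d = 15%, both arms | 34.0% vs 5.1% | 28.9 | 92.1% | 89.4% |
| d = 15%, ABSK021 only | 34% vs 6% | 28.0 | 89.1% | 85.8% |

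At 15%, 9 of 60 ABSK021 patients lack the scan, and 9 × 0.40 = 3.6 expected responders are scored as non-responders. With equal loss in both arms, power (usual p) runs from 95.6% at d = 5% to 81.7% at d = 30%.

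**The case against.** The best reply is that nothing says patients who stop leave the Week 25 schedule. Section 6.3.6 may add progression follow-up to the Part 1 visits rather than replace them, and Table 7 and SAP 6.4.2 expressly favour continued visits. This stands against any claim that the documents remove these patients from the schedule. It does not remove the gap: encouragement in the statistical sections is not a visit in the schedule, and the patient-reported outcome footnotes show that the sponsor saw the need to say so there.

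Four stronger readings are tempting and are not supported:
- **These patients automatically become non-responders.** Non-response follows only if the Week 25 MRI is missing or not evaluable. MRI is also due at end of treatment. The SAP window tables contain no MRI window, and reading procedures are deferred to the BIRC charter, so whether an off-schedule scan may count is unsettled. A progression that BIRC also calls at Week 13 is non-response whatever Week 25 shows.
- **The loss falls mainly on ABSK021.** This is possible but not shown. Protocol 1.2.2 reports no drug-related events leading to discontinuation in the Phase 1 TGCT patients as of June 2022.
- **The trial becomes underpowered.** The 15% is already built into the 90 patients. It also includes consent withdrawal and loss to follow-up, which no schedule change recovers.
- **The ROM window hides missing data.** The SAP window, "128, 1st dose date of Part 2 or 184", follows the midpoint rule in SAP 4.2.4, because ROM has only Week 13 and Week 25 visits. PRO windows start at Day 156 because PROs have a Week 21 visit. Starting ROM at Day 156 would leave Days 128–155 in no window.

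Protocol 4.3.1 strongly recommends completing Part 1 visits after progression, but only when discussing early entry into Part 2.

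**Conclusion.** The point holds as a mismatch between schedule and estimand. Four gaps support it: 12-week scans without a starting point and limited to non-PD stops; no ROM after end of treatment, although the SAP estimand uses ROM after stopping for any reason and after alternative therapy; MRI and ROM footnotes silent on Week 25 after stopping; and an unblinding rule that ends study participation without a place in Table 7.

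If 15% in both arms lacked the Week 25 scan, the expected difference would shrink by 5.1 points (34.0 to 28.9). Power under the usual two-sided p would be 92.1%, above the stated 90% and close to the 92.3% that the same convention gives for 75 evaluable patients. The 15% is an assumption, and an upper bound for this cause if the planned dropout rate is right. The calculation also assumes that a missing scan is unrelated to response. The harm is a diluted effect estimate and an analysis that does not deliver its stated estimand.

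**What to change.** 1. In Table 1 footnotes 5, 25 and 26 and in Section 6.3.6, state that patients who stop study drug in Part 1, and have neither entered Part 2 nor withdrawn consent, keep the scheduled Week 13 and Week 25 MRI and ROM, timed from randomisation. MRI after alternative anti-tumor therapy stays excluded from the primary ORR, as Table 7 says.
2. In Section 5.7.2.1, leave the treatment rule unchanged. Reconcile the requirement to leave the study with Table 7, so that unblinded patients stay in follow-up for the Week 25 assessments unless they withdraw consent.
3. Leave the ROM window in SAP Table 4.2 as it is.

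The cost is a protocol clarification, plus one re-timed MRI and one goniometer reading for a few patients. No dosing rule or unblinding criterion changes.
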